### Sample size calculation

There were around 700 new HIV infections reported in Hong Kong in 2015 and 2016. Based on previous published data, the risk of developing metabolic syndrome is approximately 20% at 96 weeks after initiation of ART, a sample size of 400 will give a 95% confidence interval from 16% to 24% at 96 weeks. Using the same 400 patients, we would be able to detect with 95% confidence an odds ratio of 2 for any risk factors with respect to the incidence of metabolic syndrome assuming that the prevalence is 20% and we would like to have an estimate of the population odds ratio to within 50% of the true value (i.e. a lower bound of 1.0 for the 95% confidence interval of the odds ratio) even after adjusted for type I error due to multiple risk factors.

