### Statistical analysis

a. The incidence rate of each HANA defined as above will be calculated as:

$$\text{incidence rate of HANA (per 100 person - years)} \\ = \frac{\text{number of new diagnosis of HANA at end of follow up}}{\text{number of persons at risk * number of years of follow up}} \times 100$$

b. The incidence rate of each HANA will be determined for subjects started INSTI-based regimens and other non-INSTI-anti-retroviral regimens.

c. Variables, including demographic, clinical, treatment-related, and laboratory parameters, will be evaluated for association with development of various HANA, in univariate and multivariate analyses. Analyses will be performed for the whole cohort, and subgroup analyses will be performed in those initiated INSTI-based regimens and other non-INSTI-based regimens.

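### The sample size section presents a precision criterion as the ability to detect an odds ratio of 2; no power is stated, and a two-group factor that only just meets the criterion has about 50% power

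*Combined protocol and SAP*

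**What the plan says.** The Sample size calculation section makes two statements about the same 400 patients.

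- **Incidence.** It takes it that "the risk of developing metabolic syndrome is approximately 20% at 96 weeks after initiation of ART", and concludes that "a sample size of 400 will give a 95% confidence interval from 16% to 24% at 96 weeks".
- **Risk factors.** It states that "we would be able to detect with 95% confidence an odds ratio of 2 for any risk factors". The reason given is that "we would like to have an estimate of the population odds ratio to within 50% of the true value", which it restates as "a lower bound of 1.0 for the 95% confidence interval of the odds ratio". It says that this holds "even after adjusted for type I error due to multiple risk factors".

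The section states no power, exposure share, number of risk factors or adjustment method. It also does not say whether 20% is the risk in the whole cohort or in the unexposed.

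Under Statistical analysis, item c, demographic, clinical, treatment-related and laboratory variables "will be evaluated for association with development of various HANA, in univariate and multivariate analyses". The Clinical hypotheses section adds a directional claim: lower incidence of these conditions on integrase inhibitor-based regimens.

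**The concern.** Evaluating a factor for association amounts to asking whether its odds ratio differs from 1. Sizing for precision answers another question: how close the estimate will lie to the truth. The section joins the two as if they were one event.

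Take a true odds ratio of 2 and a standard error that just meets the target. The estimate then falls above 1.0 about 97.5% of the time. The lower confidence limit falls above 1.0 only when the estimate itself exceeds 2, which happens about half the time. The first is what the precision target controls; the second is detection.

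This paragraph is the plan's only statement of what the study can detect, and it covers the regimen contrast as one factor among others. A reader who takes it at face value could treat a non-significant association as evidence against a doubling of the odds, which the design may not support.

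**Working it through.** **Inputs from the plan:** N = 400; 20% risk at 96 weeks; odds ratio 2; relative precision 0.50; 95% confidence interval.

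**Assumptions, because the plan is silent:** all 400 evaluable; a binary factor; two-sided 5% Wald test on the log odds ratio; 20% is the risk in the unexposed (the overall-risk reading is in step 6); Bonferroni where multiplicity is adjusted.

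**1. The plan's incidence interval.** 0.20 ± 1.96 × √(0.20 × 0.80/400) = 0.20 ± 0.039, or 16.1% to 23.9%. This reproduces the stated figure.

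**2. The precision criterion.** With p0 = 0.20 and odds ratio 2, the odds in the exposed are 2 × 0.25 = 0.5, so p1 = 1/3.

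n per group = z² × [1/(p0(1−p0)) + 1/(p1(1−p1))] / [ln(1−0.5)]² = 1.96² × (6.25 + 4.5)/0.4805 = 85.95

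That is 86 per group, 172 in total. So 400 meets the criterion for a balanced factor, with room to spare before multiplicity adjustment.

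**3. Power when the criterion is just met.** Power = Φ(ln 2/SE − z). Meeting the criterion exactly means ln 2/SE = z, so power = Φ(0) = 50%. Simulation with 86 per group gave 50.2%.

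**4. Power at N = 400, odds ratio 2.** For exposed share f, SE = √[6.25/(400(1−f)) + 4.5/(400f)]. The critical value is z = 1.960 unadjusted and 2.576 for 5 factors.

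| Exposed | SE | ln 2/SE | Expected lower 95% limit | Power, unadjusted | Power, 5 factors |
|---|---|---|---|---|---|
| 50% | 0.232 | 2.99 | 1.27 | 85% | 66% |
| 20% | 0.275 | 2.52 | 1.17 | 71% | 48% |
| 80% | 0.304 | 2.28 | 1.10 | 63% | 38% |
| 10% | 0.360 | 1.92 | 0.99 | 49% | 26% |

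With half exposed, the expected 95% interval around an odds ratio of 2 is 1.27 to 3.15. With 10% exposed, the expected lower limit is below 1.0, so even the precision criterion fails. Power below 50% always means that the matching criterion fails: at 5 factors, the 20%, 80% and 10% rows do not meet the adjusted criterion.

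**5. How many factors the adjustment can cover.** With half exposed, 17 factors need z = 2.974 and 197.9 per group, which 200 per group meets; power is Φ(2.990 − 2.974) = 51%. Eighteen factors need 200.2 per group, just over what is available. Seventeen is therefore the largest number that still meets the criterion, and power there is back to about one half.

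**6. If 20% is the overall risk.** With half exposed, p0 = 0.146, p1 = 0.254 and SE = 0.258, so ln 2/SE = 2.69. Power is 77% unadjusted and 54% for 5 factors.

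**7. The regimen contrast in the hypothesised direction.** With 20% on non-INSTI regimens and odds ratio 0.5, the INSTI odds are 0.125, so the INSTI risk is 1/9 and 1/(p(1−p)) = 10.125.

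- 50% INSTI: SE = √(6.25/200 + 10.125/200) = 0.286; power = Φ(2.42 − 1.96) = 68%.
- 80% INSTI: SE = √(6.25/80 + 10.125/320) = 0.331; power = Φ(2.09 − 1.96) = 55%.

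Both are unadjusted.

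**The case against.** The case on the other side has real force.

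- **Precision is a legitimate basis for sizing a cohort.** The first objective is to estimate incidence, and the interval for that reproduces. This stands: the fault lies in the detection wording and in equating the two events, not in sizing by precision or in the choice of 400.
- **The plan gives a confidence level, not a power.** A reader might infer that the sponsor claims 95% power and falls short of it. The text does not support that: its 95% is tied to the interval in the same sentence. Measuring the study against 95% power would be measuring it against a target that the plan does not set.
- **50% is not the power of this study.** A reader might infer that it is. It belongs to a factor that only just meets the criterion, such as a balanced one with 172 patients. At 400, a balanced unadjusted factor has about 85%.
- **Not all factors are binary.** A reader might infer that 400 patients can never reach 95% power for an odds ratio of 2. For a two-group factor this is so: the maximum over event rates and splits is 92.7%. If the odds ratio were per standard deviation of a continuous factor, power would exceed 99%. The plan does not say that it is, and the regimen contrast is binary.
- **Nothing in the plan says that null findings will be read as excluding an odds ratio of 2.** True. That is a risk the wording creates, not a stated intention.

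None of this rescues the sentence. It claims detection for any risk factor after multiplicity adjustment, and the calculation behind it has no power term.

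**Conclusion.** The concern holds in this limited form: a precision criterion is presented as a detection ability, and the detection ability is not shown. For a binary factor with 20% risk in the unexposed, unadjusted power for an odds ratio of 2 runs from about 85% (half exposed) down to 49% (10% exposed). With 5 Bonferroni-adjusted factors it runs from 66% to 26%. Factors that meet the criterion they are held to, adjusted or not, have at least 50% power, so they are missed at most about half the time; the lower figures belong to factors that fail it.

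These figures rest on exposure shares, a number of factors and an adjustment method that the plan does not give. They also assume 400 evaluable patients. Losses, or patients who already have metabolic syndrome at baseline, would reduce that number; the plan gives no figures for either.

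The documents do not support going further and saying that the sample size is wrong or that the plan misstates a power. The sentence should be corrected; the design need not change.

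**What to change.** In the Sample size calculation section:

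1. Delete the claim of detection with 95% confidence, its extension to any risk factor, and the clause that equates precision with a lower limit of 1.0.
2. State the expected precision on its own, for example a 95% confidence interval of 1.27 to 3.15 for an odds ratio of 2 with half exposed.
3. State the power separately, over a declared range of exposure shares and numbers of adjusted factors. Name the adjustment method and label these inputs as assumptions.
4. Say whether 20% is the risk in the unexposed or in the whole cohort.
5. Add the corresponding line for the INSTI contrast.

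Under Statistical analysis, state that non-significant associations will be interpreted from their confidence intervals and not reported as excluding an odds ratio of 2.

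The cost is one reworded paragraph and one added sentence. Enrolment and procedures do not change, and N stays at 400. The downside is that the stated detection ability will look less favourable.

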### Statistical analysis

a. The incidence rate of each HANA defined as above will be calculated as:

$$\text{incidence rate of HANA (per 100 person - years)} \\ = \frac{\text{number of new diagnosis of HANA at end of follow up}}{\text{number of persons at risk * number of years of follow up}} \times 100$$

b. The incidence rate of each HANA will be determined for subjects started INSTI-based regimens and other non-INSTI-anti-retroviral regimens.

c. Variables, including demographic, clinical, treatment-related, and laboratory parameters, will be evaluated for association with development of various HANA, in univariate and multivariate analyses. Analyses will be performed for the whole cohort, and subgroup analyses will be performed in those initiated INSTI-based regimens and other non-INSTI-based regimens.

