### **Objectives**

- To determine the incidence of HANA conditions in newly diagnosed HIV-infected individuals initiating integrase inhibitor-based and other anti-retroviral regimens in an Asian population
- To evaluate the risk factors associated with developing each HANA condition
- To set up an electronic platform for systematic collection of clinical data and establishment of a clinical decision tool for clinical risk prediction and improvement in clinical management

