### **Clinical hypotheses**

Individuals initiating integrase inhibitor-based anti-retroviral regimens will develop lower incidence of HANA.

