## **Data collection and investigations**

- a. Eligible subjects will attend Infectious Diseases clinic at the Prince of Wales Hospital for assessment.

The first study visit will be scheduled before or within four weeks of initiation of ART. Annual visits will be scheduled thereafter for 5 years. During each study visit, demographic and clinical data will be collected. Physical examination will be performed. Blood and urine tests will be done at fasting state. Imaging, including ultrasonography of carotid arteries, DEXA scan and fibroscan, will be performed. Stool samples will be collected for microbiota study.

- b. Clinical data

A structured standardized research tool will be used to collect demographic and clinical data:

1. Age, gender, smoking status, alcohol consumption, exercise
2. Co-morbid illnesses, including history or new diagnoses of hepatitis B and C, diabetes, dyslipidemia, hypertension, metabolic syndrome, and cardiovascular diseases, as well as all comorbidities included in the Charlson comorbidity score
3. Date of HIV diagnosis, latest CD4 counts, latest HIV viral load
4. Medication history, including anti-retroviral drugs and other medications

- c. Physical examination and anthropometric measurements

1. Body weight and height, and body mass index
2. Hip and waist circumferences
3. Blood pressure
4. For subjects aged  $\geq 50$  years old, assessment of frailty, including hand grip strength, balance tests, 6-metre walking speed, will be performed
5. Neurocognitive assessment
  - i. International HIV dementia scale  
<https://www.hiv.uw.edu/page/mental-health-screening/ihds>
  - ii. Montreal Cognitive Assessment
  - iii. Symbol digit modality test (SDMT)
  - iv. Action fluency: ask the patient to say as many things that people do in 1 minute
  - v. Cogstate platform neurocognitive tests
  - vi. DASS 21 for screening of mood
  - vii. Lawton Instrumental Activities of Daily Living
6. Quality of life assessment
  - i. EQ-5D-5L questionnaire
7. Lung function test
  - i. FEV1 and FVC will be performed in smokers.

- d. Blood tests:

The following blood tests will be performed after an 8-hour fast:

1. Glucose, insulin, HbA1c
2. Total cholesterol, LDL cholesterol, HDL cholesterol, triglyceride, apolipoprotein A and apolipoprotein E
3. Complete blood count, creatinine, urate, calcium, phosphate, urea, ferritin

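### The incidence-rate formula in item a does not define person-time; taken literally as baseline head count times 5 years, it gives rates that are too low, most of all for common conditions

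*Combined protocol and SAP*

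**What the plan says.** The protocol and SAP define the incidence rate once, in item a of Statistical analysis, for every HIV-associated non-AIDS (HANA) condition. The numerator is "number of new diagnosis of HANA at end of follow up". The denominator is "number of persons at risk * number of years of follow up". The quotient is multiplied by 100 and labelled per 100 person-years.

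Item b applies the same rate by regimen: "The incidence rate of each HANA will be determined for subjects started INSTI-based regimens and other non-INSTI-anti-retroviral regimens".

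On follow-up, Data collection and investigations says "Annual visits will be scheduled thereafter for 5 years". No section says when the persons at risk are counted, whether the years are individual, mean or planned, or when a person stops contributing time.

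The rate serves the first-listed objective, "To determine the incidence of HANA conditions in newly diagnosed HIV-infected individuals", and bears on the clinical hypothesis, "Individuals initiating integrase inhibitor-based anti-retroviral regimens will develop lower incidence of HANA".

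**The concern.** A person-time rate needs each participant's time to stop when that participant is no longer at risk of a first diagnosis. Item a has the unit of such a rate but not the construction. With visits fixed for 5 years, the literal product is the number at risk at baseline times 5. This credits everyone with 5 years, including someone diagnosed at the first annual visit.

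The result is cumulative incidence divided by 5, under a person-years label. It is too low whenever anyone is diagnosed before year 5, and the shortfall grows with frequency. Several definitions under Outcome measures have low thresholds (blood pressure from 130/80 mmHg, BMI above 23, GFR below 90), so some conditions may well be common.

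Two analysts could follow item a on identical data and report different rates for the first objective. Anyone comparing the two regimen rates from item b would also see a ratio pulled toward 1 when follow-up is equal.

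**Working it through.** **Inputs from the plan.** N = 400; 5 years of annual visits; for metabolic syndrome, "the risk of developing metabolic syndrome is approximately 20% at 96 weeks after initiation of ART". The same paragraph of Sample size calculation later works from "assuming that the prevalence is 20" per cent, so it is not certain that the whole 20% is incident.

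**The plan's own figure.** 0.20 ± 1.96 × √(0.20 × 0.80 / 400) = 0.20 ± 0.039, or 16.1% to 23.9%. This agrees with the stated 16% to 24%. That interval concerns a proportion and does not use item a.

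**Assumptions for the illustration.** All 400 are free of the condition at baseline (the percentages do not depend on this number), there is no dropout, and the 20% is all incident.

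**Formulas.** t0 = 96 weeks = 1.840 years. λ = −ln(0.8)/1.840 = 0.1213 per year up to week 96, then f × λ to year 5.
- Proportion diagnosed: D = 1 − 0.8 × exp(−fλ(5 − t0)).
- Years at risk per person: P = 0.2/λ + 0.8 × [1 − exp(−fλ(5 − t0))]/(fλ); the last term is 0.8 × (5 − t0) when f = 0.
- Person-time rate = D/P. Head-count rate = D/5. Shortfall = 1 − P/5.
- With onset dated at the detecting visit, P becomes S(0)+S(1)+S(2)+S(3)+S(4), where S(k) is the proportion still undiagnosed at year k.

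The head-count denominator is 400 × 5 = 2,000 person-years in every row. Rates are per 100 person-years.

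| Hazard after week 96 | Diagnoses | Person-years (exact onset) | Person-time rate | Head-count rate | Shortfall, exact onset | Shortfall, visit-dated |
|---|---|---|---|---|---|---|
| Zero | 80.0 | 1,670.9 | 4.79 | 4.00 | 16.5% | 14.3% |
| A quarter | 109.2 | 1,623.9 | 6.73 | 5.46 | 18.8% | 15.9% |
| Half | 135.8 | 1,579.9 | 8.60 | 6.79 | 21.0% | 17.5% |
| Unchanged | 181.9 | 1,499.6 | 12.13 | 9.09 | 25.0% | 20.4% |
| 1.5 times | 219.9 | 1,428.7 | 15.39 | 11.00 | 28.6% | 23.0% |
| Twice | 251.3 | 1,365.9 | 18.40 | 12.57 | 31.7% | 25.3% |

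Visit dating, unchanged hazard: 1 + 0.886 + 0.785 + 0.695 + 0.616 = 3.981 years per person, and 1 − 3.981/5 = 20.4%.

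**Midpoint dating.** Take D/2 off the visit-dated years. The rate is 12.11 against an exact 12.13 (unchanged hazard), or 4.78 against 4.79 (zero hazard). The head-count shortfall is then 24.9% or 16.3%.

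**If less of the 20% is incident (assumed, exact onset).** With 10% incident by week 96, the shortfall is 8.2% (zero later hazard) to 13.0% (unchanged). With 5%, it is 4.1% to 6.7%.

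**Rare condition (assumed 1 per 100 person-years).** 1 − (1 − exp(−0.05))/0.05 = 2.5%.

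**Regimen ratio (assumed hazard ratio 0.50, equal follow-up, no loss).** The head-count ratio is D at λ/2 over D at λ. With an unchanged hazard it reads 0.575, where person-time gives 0.50. With no cases after week 96 it reads 0.528, where person-time gives 0.48.

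**The case against.** The strongest reply is that the formula is textbook shorthand. The unit is person-years, and someone already diagnosed is no longer at risk, so summed individual time may be what was meant. If so, there is no bias and item a only needs to say it. A yearly re-count of those at risk is also sound: its denominator, S(0) to S(4), is person-time with diagnoses dated at the detecting visit. This stands as a limit on the claim. The bias follows from the head-count reading, and the documents do not show that the analysts will adopt it. It does not remove the defect, because the written product states neither alternative.

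The size is also conditional. The 16% to 25% needs the whole 20% to be incident, a hazard after week 96 that does not rise, and exact or midpoint onset dating. The documents settle none of these, so the figures are an illustration.

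A reader might infer larger errors from dropout. If lost participants were charged the full 5 years, assumed losses of 5% to 10% a year would give shortfalls of 26% to 40%. Unequal losses of 10% against 2% (constant hazard) would make equal true rates read as a ratio of 0.84 or 1.19. The documents give no loss rate, and charging 5 years to someone who left strains the words years of follow-up. On observed years the shortfall stays at about 16% to 24%.

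Lastly, item b plans no ratio, test or interval, so the pull toward 1 affects a comparison that a reader would make, not a planned analysis.

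**Conclusion.** Item a is wrong as written: it carries a person-years label, but its denominator never ends a person's time. Read literally, it reports 5-year cumulative incidence divided by 5. Without dropout that is always below the person-time rate, slightly for rare conditions and materially for common ones.

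For metabolic syndrome the size depends on inputs that the plan leaves open. It is 16% to 25% with exact or midpoint dating, or 14% to 20% with visit dating, if the 20% is all incident and the later hazard is constant or falls. It is 4% to 13% if only 5% to 10% is incident. With exact dating it exceeds 25% if the hazard rises.

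Two stronger conclusions do not follow. One is that the study's rates will be wrong by these amounts; a person-time reading remains open and has no such bias. The other is that the regimen analyses or the sample size are undermined; the association analyses in item c and the sample size do not rest on this rate. The case for action is that the only stated formula for the first-listed objective admits different answers, its literal reading is biased, and the repair is cheap.

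**What to change.** Replace the denominator in item a with the sum, over participants free of that condition at baseline, of time from baseline to the earliest of first diagnosis, death, last assessed visit or year 5.

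State one rule for dating diagnoses found at annual visits, either the midpoint between the last negative and first positive visit or the detecting visit itself, and apply it identically in both regimen groups. Use the same person-time for the rates in item b. If a 5-year proportion is wanted, report it separately as cumulative incidence.

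The cost is one formula, one dating rule and a few lines of analysis code using visit dates. No visit, measurement or eligibility rule changes. Data collection and investigations does not list visit dates by name, so confirm that the database holds them.

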### **Study design**

This is a prospective, longitudinal, cohort study. 400 newly diagnosed HIV-infected individuals attending HIV clinics in Hong Kong will be recruited. Clinical assessment, and laboratory and imaging studies will be performed at baseline prior to initiation of anti-retroviral regimen, than annually thereafter for 5 years. Choice of anti-retroviral regimen will be decided by the in-charge HIV physician. Incidence of development of various HANA conditions will be determined for those initiated INSTI-based regimens and other anti-retroviral regimens. An electronic platform will be used to formulate risk prediction for various clinical outcomes, and serve as a clinical decision support tool.

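### Separate risk-factor models in the INSTI and non-INSTI groups do not test whether a factor acts differently by regimen, and the multiplicity allowance covers far fewer factors than the laboratory panel could supply

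*Combined protocol and SAP*

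**What the plan says.** Item c of the Statistical analysis section relates demographic, clinical, treatment-related and laboratory variables to each HANA condition "in univariate and multivariate analyses". It does this for the whole cohort and then adds that "subgroup analyses will be performed in those initiated INSTI-based regimens and other non-INSTI-based regimens". The section gives no candidate list, limit on model size or multiplicity method, and no test of whether a factor's effect depends on regimen.

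The Sample size calculation section takes it that "the risk of developing metabolic syndrome is approximately 20% at 96 weeks after initiation of ART" and states that "a sample size of 400 will give a 95% confidence interval from 16% to 24% at 96 weeks". It then says that the same 400 patients allow the study to "detect with 95% confidence an odds ratio of 2 for any risk factors with respect to the incidence of metabolic syndrome". The criterion is "a lower bound of 1.0 for the 95% confidence interval of the odds ratio", and the claim is said to hold "even after adjusted for type I error due to multiple risk factors". Neither the number of factors nor the correction is stated, and the regimen groups are not sized.

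Item d of Data collection and investigations lists 47 distinct blood items (blood count and immunoglobulins counted once each, the repeated calcium counted once).

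**The concern.** Two models fitted in two groups give two sets of estimates and no comparison between them. Readers will compare them anyway, usually by noting which factors are significant in one group only. That comparison is unreliable when each group has few events, and more so when the groups differ in size. Regimen is chosen by the physician, so an uneven split is quite possible.

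The allowance for multiple risk factors is the plan's only protection against chance findings. If it covers a handful of factors while the panel can supply dozens, the claim gives more reassurance than it should.

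At stake is the second objective, the risk factors for each condition. The study could report factors as specific to one regimen when they act equally in both.

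**Working it through.** **Inputs.** N = 400 (Study design). Risk 20% at 96 weeks, odds ratio 2 and a 95% interval with lower bound 1.0 (Sample size calculation). 47 blood items (Data collection and investigations, d). Assumed, because the documents do not give them: regimen split, exposure prevalence, and Bonferroni as the correction.

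**1. The plan's own figures.** 0.20 ± 1.96 × √(0.20 × 0.80/400) = 0.20 ± 0.039, or 16.1% to 23.9%. This reproduces the stated interval.

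For an odds ratio of 2 to within 50%, n per exposure group = 1.96²/(ln 0.5)² × [1/(p₁(1−p₁)) + 1/(p₀(1−p₀))].
- 20% risk in the unexposed (33.3% in the exposed): the bracket is 4.50 + 6.25 = 10.75, so n = 86 per group, 172 in total.
- 20% risk overall (25.4% and 14.6%): the bracket is 5.27 + 8.03 = 13.31, so n = 107 per group, 214 in total.

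So 400 is enough for one evenly split factor.

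**2. How many factors 400 covers.** An observed odds ratio of 2 has z = ln 2/√(4.50/n₁ + 6.25/n₀), where n₁ and n₀ are the exposed and unexposed numbers; with 20% overall the two terms are 5.27 and 8.03. The Bonferroni-adjusted lower bound stays at or above 1.0 for up to 0.05/p factors.

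| Exposure | 20% risk applies to | z | p | 0.05/p |
|---|---|---|---|---|
| 50% | overall | 2.69 | 0.0072 | 6.9 |
| 50% | unexposed | 2.99 | 0.0028 | 17.9 |
| 20% | unexposed | 2.52 | 0.0118 | 4.2 |
| 10% | unexposed | 1.92 | 0.054 | 0.9 |

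That is about 7 to 17 factors at even exposure, 4 at 20% exposure and none at 10%. For 47 factors z rises to 3.27, and the total needed at even exposure is 480 (20% in the unexposed) to 594 (20% overall).

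**3. Events after the split.** 400 × 0.20 = 80, if all are at risk at baseline and none are lost. The non-INSTI group has 80 × 0.5 = 40, 80 × 0.2 = 16 or 80 × 0.1 = 8 events at INSTI shares of 50%, 80% and 90%.

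**4. False appearance of a difference.** Take a factor with odds ratio 2 in both regimens, 50% exposure and 20% risk overall. Power in a group of size n is Φ(ln 2/√(13.31/(n/2)) − 1.96).
- 50:50 split: 0.476 in each group. Significant in exactly one: 2 × 0.476 × 0.524 = 0.50.
- 80:20 split: 0.671 and 0.224. Significant in exactly one: 0.671 × 0.776 + 0.224 × 0.329 = 0.59.

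**5. Sensitivity to longer follow-up.** If the 96-week hazard stayed constant for 5 years (an assumption), the rate is −ln(0.8)/(96/52.18) = 0.121 per year, and events are 400 × (1 − e^(−5 × 0.121)) ≈ 182. With that overall risk of 45.5%, the exposed and unexposed risks are 54.0% and 37.0% and the bracket is 8.32. Power is 0.671 in each group at 50:50, and 0.860 and 0.330 at 80:20. The chance of significance in exactly one group is then 2 × 0.671 × 0.329 = 0.44 at 50:50, and 0.860 × 0.670 + 0.330 × 0.140 = 0.62 at 80:20.

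**6. What an interaction test can do.** With odds ratio 2 in the INSTI group and 1 in the other, at 20% risk, the standard error of the log ratio of odds ratios is √(13.31/100 + 12.5/100) = 0.508 at 50:50 and √(13.31/160 + 12.5/40) = 0.629 at 80:20. Power is Φ(ln 2/0.508 − 1.96) = 28% and Φ(ln 2/0.629 − 1.96) = 20%. The ratio detectable with 80% power is exp(2.80 × 0.508) ≈ 4.2 and exp(2.80 × 0.629) ≈ 5.8.

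**The case against.** The strongest reply is that neither the Objectives nor the Clinical hypotheses ask whether risk factors differ by regimen, so the subgroup models could be purely descriptive. That is fair as far as it goes. But the plan does not label them descriptive, and side-by-side models invite exactly this comparison.

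Second, the remedy is itself weak, since the interaction tests have 20% to 28% power. This stands, and it is why they should be few and exploratory. Low power is still better than a comparison that suggests a difference about half the time when there is none.

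Third, 80 is a 96-week count and follow-up is 5 years. This also stands. More events ease the problem without removing it (step 5), while baseline cases, dropout and rarer conditions work the other way.

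A reader might go further in three ways that the documents do not support:
- *That all 47 blood items enter one model, at 80/47 = 1.7 events per variable.* The list is of tests collected. No section puts them all in one model, and several of them define outcomes.
- *That the smaller regimen group cannot support any multivariable model.* At 50:50 it has 40 events, which allows about 4 parameters at 10 events each (an assumed convention). The statement becomes plausible only at very uneven splits.
- *That the clinical decision tool would rest on these models.* Item j of Data collection and investigations names existing risk scores and cut-offs, and the Electronic platform section issues reports after every visit, including early ones. No section says that the tool is built from the item c models.

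**Conclusion.** The concern holds in a limited form. The planned subgroup models cannot show whether a factor acts differently by regimen. With equal effects in both regimens they would suggest a difference about 50% to 59% of the time at splits from 50:50 to 80:20, for a binary factor with odds ratio 2, 50% exposure and 20% overall risk.

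The multiplicity claim is sound for one evenly split factor and, under Bonferroni, for about 7 to 17. It does not extend to rarer exposures, or to the full blood panel if all of it is screened. It would be wrong to infer that the claim is simply false. It is unqualified, and its limits depend on the correction, the exposure prevalence and whether the 20% is the overall or the unexposed risk; the documents fix the 20% as a cohort figure and leave the first two open.

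The change should be made before analysis. It does not call the design or the overall incidence estimates into question.

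**What to change.** In item c of the Statistical analysis section:
- For each HANA outcome, fit one whole-cohort model that includes regimen, in place of separate models by regimen.
- Assess regimen differences only through regimen-by-factor interaction terms for a short list named in advance. Report them with confidence intervals and label them exploratory. Take any within-regimen estimates from the same model and call them descriptive.
- Limit the number of model parameters to what the observed events for that outcome support.
- Leave out covariates that define the outcome, for example BMI for obesity. Smoking needs the same thought for airway disease, since lung function is measured only in smokers.

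In the Sample size calculation section, state the correction, the number of factors and the exposure prevalence for which the odds-ratio-of-2 claim holds.

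The cost is a change of wording and modest programming, with no new data. The downside is that the interaction tests will miss most two-fold differences and fewer factors will be reported as regimen-specific.
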